6.3.6. Pregnancy

For female subjects, serum pregnancy test will be performed at visit 1, and urine pregnancy test will be performed before the first dose of each regimen and biweekly during follow up visits.

Action to Be Taken if Pregnancy Occurs in a Female

If any female subject or the female partner of a male subject who becomes pregnant while participating in this study that is after enrolment until the last follow up visit, the following procedures will be followed:

- The subject must be immediately discontinued from study drug.
- The subject must be referred to antenatal clinic for follow up.
- The pregnancy will be monitored to determine the outcome of the pregnancy. Any premature termination of the pregnancy will be reported.

While pregnancy itself is not considered to be an AE or SAE, any pregnancy complication or elective termination of a pregnancy for medical reasons will be recorded as an AE or SAE (see AE/SAE section of the protocol for definitions and a description of monitoring).

A spontaneous abortion is always considered to be an SAE and will be reported as such. Furthermore, any SAE occurring as a result of a post-study pregnancy and is considered reasonably related to the investigational product by the investigator, will be reported. All pregnancies occurring during the study period and including follow up period should be reported to PI as soon as possible.

6.4. Pharmacokinetics

Blood for pharmacokinetic assessments may be obtained by individual needle stick or IV

cannula. If a cannula is used for collection of the whole blood samples, the cannula will be inserted into an arm vein within sufficient time before dosing and may be kept patent using a dilute heparin solution as a flush. An initial volume of approximately 1.0 mL of blood will be collected and discarded prior to collection of each whole blood sample to ensure that the saline or heparin solution does not artificially dilute the samples. If PK samples are collected via individual needle sticks rather than through a cannula, then no extra blood needs to be collected and discarded prior to the collection of the sample.

Each blood sample will be labeled with subject's number, schedule date and time, collection date and time. The actual time of each blood sample will be recorded on the case report form (CRF).

Regimen	Blood sampling	ECG measurements
Regimen 1: Artemether- lumefantrine (AL) Dosing: 0h, 8h, 24 h, 36 h, 48 h, 60 h	 Day 0: Hr. 0 (pre-dose), 0.25, 0.5, 1, 2, 3, 4, 6, 8 (pre-dose), 10, 12, 14 Day 1: Hr. 24 (pre-dose), 26, 28, 30, 36 (pre-dose), 38, 40, 42 Day 2: Hr. 48 (pre-dose), 48.25, 48.5, 49, 50, 51, 52, 54, 56, 60 (pre-dose), 61, 62, 64, 66 Day 3: Hr. 72 Day 4, Day 7, Day 14, Day 28 	Day -1: Hr. 0, 1, 2, 4, 6, 8, 10, 12, 14 Day 0: Hr. 0 (pre-dose), 1, 2, 4, 6, 8 (pre-dose), 10, 12, 14 Day 1: Hr. 24 (pre-dose), 26, 28, 30, 36 (pre-dose), 38, 40, 42 Day 2: Hr. 48 (pre-dose), 49, 50, 52, 54, 60 (pre-dose), 61, 62, 64, 66 Day 3: Hr. 72 Day 4, Day 7, Day 14, Day 21, Day 28
Regimen 2: Amodiaquine (AQ) Dosing: 0h, 8h, 24 h, 36 h, 48 h, 60 h	Day 0: Hr. 0 (pre-dose), 0.25, 0.5, 1, 2, 3, 4, 6, 8 (pre-dose), 10, 12, 14 Day 1: Hr. 24 (pre-dose), 26, 28, 30, 36 (pre-dose), 38, 40, 42 Day 2: Hr. 48 (pre-dose), 48.25, 48.5, 49, 50, 51, 52, 54, 56, 60 (pre-dose), 61, 62, 64, 66 Day 3: Hr. 72 Day 4, Day 7, Day 14, Day 28, Day 42	Day -1: Hr. 0, 1, 2, 4, 6, 8, 10, 12, 14 Day 0: Hr. 0 (pre-dose), 1, 2, 4, 6, 8 (pre-dose), 10, 12, 14 Day 1: Hr. 24 (pre-dose), 26, 28, 30, 36 (pre-dose), 38, 40, 42 Day 2: Hr. 48 (pre-dose), 49, 50, 52, 54, 60 (pre-dose), 61, 62, 64, 66 Day 3: Hr. 72 Day 4, Day 7, Day 14, Day 21, Day 28, Day 35, Day 42
Regimen 3: Artemether- lumefantrine + amodiaquine (AL+AQ)	Day 0: Hr. 0 (pre-dose), 0.25, 0.5, 1, 2, 3, 4, 6, 8 (pre-dose), 10, 12, 14 Day 1: Hr. 24 (pre-dose), 26, 28, 30, 36 (pre-dose), 38, 40, 42 Day 2: Hr. 48 (pre-dose), 48.25, 48.5,	Day -1 : Hr. 0, 1, 2, 4, 6, 8, 10, 12, 14 Day 0 : Hr. 0 (pre-dose), 1, 2, 4, 6, 8 (pre-dose), 10, 12, 14 Day 1 : Hr. 24 (pre-dose), 26, 28, 30, 36

Table 2 Pharmacokinetic collection schedule for each study regimens

Dosing: 0h, 8h, 24 h, 36 h, 48 h,	49, 50, 51, 52, 54, 56, 60 (pre-dose), 61, 62, 64, 66 Day 3 : Hr. 72	(pre-dose), 38, 40, 42 Day 2 : Hr. 48 (pre-dose), 49, 50, 52, 54, 60 (pre-dose), 61, 62, 64, 66	
60 h	Day 4, Day 7, Day 14, Day 28, Day 42	Day 3 : Hr. 72	
		Day 4, Day 7, Day 14, Day 21, Day 28, Day 35, Day 42	

The time-window for the visit on Day 4 is + 1 day and for the visits on Days 7 - 42 is + 2 or - 2 days

Total blood collection for pharmacokinetic analysis will be around 165 mL.

The total blood collections for both laboratory assessments and pharmacokinetic sampling on each visit was summarized in Appendix 4.

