Amodiaguine by oral administration is absorbed rapidly, and then extensively metabolized to N-desethylamodiaquine (active metabolite) and 2-hydroxy-desethyl-amodiaquine by hepatic first-pass effect. C_{max} of amodiaguine in plasma, whole blood and packed cells is 32±3ng/ml, 60±10ng/ml and 42±6ng/ml respectively; Tmax of amodiaguine is 0.5±0.03h, 0.5±0.1h and $0.5\pm0.1h$ respectively; AUC₀₋₈ of amodiaguine in plasma, whole blood and packed cells is 99 ± 19 ng·ml⁻¹h, 148 ± 25 mJ⁻¹h and 167 ± 72 ng·ml⁻¹h respectively. Cmax of desethylamodiaguine in plasma, whole blood and packed cells is 181±26ng/ml (19 fold higher than those of the parent drug), 561±70ng/ml and 561±143ng/ml respectively; Tmax for desethylamodiaguine is 3.4±0.8h, 2.2±0.5h and 3.6±1.1h respectively; and AUC0-24 for desethylamodiaquine in plasma, whole blood and packed cells is 2304±37ng·ml⁻¹h, 6811±752ng·ml⁻¹h and 5713±1269ng·ml⁻¹h respectively (whole blood AUC was higher than plasma AUC, P<0.001). The trial of ¹⁴C-labelled amodiaquine administered orally to Wistar rats showed that amodiaquine can be distributed widely in body with the main organs of accumulation being kidney, liver, bone marrow and spleen. Amodiaquine is not observed in plasma 8 hours after administration, whereas the concentration of desethylamodiaquine in plasma at 96h is 29 ± 8 ml⁻¹. The half-life of amodiaguine in plasma is 5.2 ± 1.7 h, and elimination half-life ($\beta_{t1/2}$) of desethylamodiaquine in plasma is 9-31 days. The bioavailability of amodiaquine is decreased due to first-pass hepatic metabolism. The plasma protein binding rate of amodiaguine and desethylamodiaguine is greater than 90%. The T_{max} of amodiaguine taken orally by patients with falciparum malaria is 1.75h, distinctly longer than the T_{max} of healthy volunteers (18).

Potential interactions through hepatic metabolism

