12.5 Methods of statistical analysis

12.5.1 Pharmacokinetic assessments

Individual concentration-time data will be evaluated using a non-compartmental analysis approach as implemented in WinNonlin (Pharsight Corporation, California, USA). Total exposure up to the last measured concentration (AUC_{0-LAST}) will be calculated using the linear trapezoidal method for ascending concentrations and the logarithmic trapezoidal method for descending concentrations. Exposure will be extrapolated from the last observed concentration to time infinity by C_{LAST}/λ_Z for each individual subject to compute total drug exposure (AUC_{0- ∞}). The terminal elimination half-life (t_{1/2}) will be estimated by log-linear regression of the terminal phase. Maximum plasma concentration (C_{MAX}) and time to maximum concentration (T_{MAX}) will be taken directly from the observed data. Apparent volume of distribution (V_D/F) and oral clearance (CL/F) will be computed individually according to standard procedures and summarized for each treatment arm.

Pharmacokinetic parameters (i.e. AUC_{0-LAST}, AUC_{0- ∞}, C_{MAX}, T_{MAX}, CL/F, V_D/F, and t_{1/2}) will be described using means (SD or 95% CI) and medians (range) as appropriate.

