3.5.2 Pharmacokinetic assessments

Individual pharmacokinetic parameters of artemether/dihydroartemisinin, lumefantrine/desbutyl-lumefantrine and amodiaquine/desethylamodiaquine will be calculated after each dose administration using a non-compartment approach.

Total exposure up to the last measured concentration (AUC_{LAST}) will be calculated using the linear trapezoidal method for ascending concentrations and the logarithmic trapezoidal method for descending concentrations. The terminal elimination half-life ($t_{1/2}$) will be estimated by the slope (λ_Z) of the best-fit log-linear regression of the observed concentrations in the terminal elimination phase. Drug exposure will be extrapolated from the last observed concentration to time infinity by C_{LAST}/λ_Z for each individual subject to compute total drug exposure (AUC_{∞}). Maximum concentration (C_{MAX}) and time to maximum concentration (T_{MAX}) will be taken directly from the observed data. Apparent oral elimination clearance (CL/F) and apparent volume of distribution (V/F) will be computed individually according to the equations below.

$$CL/F = \frac{Dose}{AUC_{\infty}} \quad V/F = \frac{t_{1/2} \times CL/F}{\ln 2}$$

The pharmacokinetic parameters will be summarised for each drug stratified by arm (i.e., when administered alone or in combination). Similarly, descriptive statistics will be summarised by arm. Ln-transformed pharmacokinetic exposure parameters (C_{MAX} , AUC_{LAST} and AUC_{∞}) will be evaluated to assess potential drug-drug interactions. No drug-drug interaction is assumed if the 90% confidence intervals of the ratio (combination/alone) of C_{MAX} , AUC_{LAST} and AUC_{∞} fall within 80% to 125% [10]. The 90% confidence intervals of the ratio (combination (COMB)/alone (ALONE)) will be calculated according to equation below.

$$Mean\ ratio\ (\%) = 100 \cdot e^{Parameter_{combination} - Parameter_{alone}}$$

where $Parameter_{combination}$ and $Parameter_{alone}$ are the least square mean of the natural logarithm of parameters derived for the combination and alone administration, respectively. The upper and lower boundary of the 90% confidence interval are calculated as follow:

$$90\% \ Confidence\ Interval = 100 \cdot e^{(Parameter_{combination} - Parameter_{alone}) \pm t_{0.95} \cdot SE_D}$$

STATISTICAL ANALYSIS PLAN FOR ALAQ STUDY

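### Four of the six amodiaquine doses have no sample near the documented 0.5 h peak, so full-profile AUC is probably understated and the combination/alone ratio would shift if co-administration changed absorption speed

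*Protocol*

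**What the plan says.** Protocol 6.4, Table 2, gives the same dosing times for every regimen: "Dosing: 0h, 8h, 24 h, 36 h, 48 h, 60 h". The within-admission sampling times are also common to all three:

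- First day: "Day 0: Hr. 0 (pre-dose), 0.25, 0.5, 1, 2, 3, 4, 6, 8 (pre-dose), 10, 12, 14"
- Second day: "Day 1: Hr. 24 (pre-dose), 26, 28, 30, 36 (pre-dose), 38, 40, 42"
- Third day: "Day 2: Hr. 48 (pre-dose), 48.25, 48.5, 49, 50, 51, 52, 54, 56, 60 (pre-dose), 61, 62, 64, 66"

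The Introduction (amodiaquine data) reports for plasma: "Tmax of amodiaguine is 0.5±0.03h", Cmax 32 ng/mL, AUC0-8 99 ng·h/mL and half-life 5.2 h. It adds that Tmax "taken orally by patients with falciparum malaria is 1.75h".

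Protocol 12.5.1 says exposure up to the last measured concentration "will be calculated using the linear trapezoidal method for ascending concentrations and the logarithmic trapezoidal method for descending concentrations", and SAP 3.5.2 repeats the rule. SAP 3.5.2 then sets the decision: "No drug-drug interaction is assumed if the 90% confidence intervals of the ratio (combination/alone") for Cmax, AUC-last and AUC-infinity lie within 80-125%. It derives CL/F as dose over AUC-infinity. It also says that parameters are worked out following each administration, without saying whether AUC is per dose or over all six doses.

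**The concern.** Samples at 0.25 and 0.5 h exist only after the first and fifth doses. For the other four, the linear-up rule joins the pre-dose trough to a first sample taken at 2 h (or 1 h after the last dose), well past a 0.5 h peak. The area above that line is lost.

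The loss depends on how fast the drug is absorbed. It is largest for an early, sharp peak and shrinks as the peak moves towards 2 h. It therefore divides out of the combination/alone ratio only if artemether-lumefantrine leaves amodiaquine absorption unchanged. If absorption slows, less area is lost in the combination and the ratio rises with no real change in exposure. The same shift could hide a real fall in exposure. Amodiaquine AUC is a primary endpoint. CL/F and V/F, which are secondary, are overstated in any case.

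**Working it through.** The plan states no AUC error, CV or power, so there is no figure of its own to reproduce.

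**Step 1: count samples.** Samples strictly within the first hour after doses 1 to 6 number 2, 0, 0, 0, 2, 0. The 0.5 h peak is unsampled after four of six doses.

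**Step 2: model.** For one dose, C(t) is the sum over (A, x) = (F, α) and (1−F, β) of A·ka/(ka−x)·(e^(−xt) − e^(−ka·t)). Here β = ln 2/5.2, and F and ka are solved so that Tmax = 0.5 h and AUC0-8/Cmax = 99/32 = 3.09. The distribution rate α is not in the documents; I assumed 0.5 to 2.0 per h. Six doses were superposed, and the linear-up/log-down AUC at the 35 planned times was compared with a fine-grid integral to 72 h.

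| α (per h) | AUC0-72 error |
|---|---|
| 0.5 | −14.5% |
| 0.8 | −13.4% |
| 1.2 | −12.9% |
| 2.0 | −12.6% |

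By dosing interval the error is about −1% (dose 1), −18 to −22% (dose 2), −23 to −26% (dose 3), −22 to −25% (dose 4), under −1% (dose 5) and −9 to −10% (dose 6). CL/F is too high by 1/(1−0.126) = 1.144 to 1/(1−0.145) = 1.170, that is 14-17%.

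**Step 3: sensitivity of the AUC error.**

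- Peak already at 1.0 h: about −7 to −10%. At 1.75 h: about −4%.
- AUC0-8 and half-life each moved by one documented SD: −9 to −23%.
- One compartment with half-life 5.2 h: −7%, but this implies AUC0-8 near 167, not 99.
- Concentrations from 8 h after a dose set to zero, compared with a dense schedule treated the same way: −15 to −16%.
- Desethylamodiaquine and lumefantrine: under 1%. Artemether, as one compartment with half-life 2 h and an assumed peak at 1.2-1.9 h: 6-10% low.
- Amodiaquine Cmax: observed/true about 0.96-0.97, because doses 1 and 5 are densely sampled.

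**Step 4: effect on the ratio.** Absorption alone was slowed, with clearance and bioavailability held fixed.

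| Combination | Observed ratio | True AUC0-72 ratio |
|---|---|---|
| Same absorption as alone | 1.00 | 1.00 |
| Tmax 1.0 h | about 1.06 | 1.00 |
| Tmax 1.75 h | 1.09-1.11 | 0.99-1.00 |
| 0.5 h lag | 1.07-1.09 | 1.00 |
| 1 h lag | 1.10-1.12 | about 0.99-1.00 |

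On the log scale, 1.06 uses ln 1.06/ln 1.25 = 0.058/0.223 = 26% of the upper margin, and 1.11 uses 0.104/0.223 = 47%.

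**Step 5: can it change the decision?** The documents give no within-subject CV, so I assumed 15% and 25%, with 16 paired subjects and t(0.95, 15) = 1.753. The half-width on the log scale is 1.753·√(ln(1+CV²))·√(2/16).

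- CV 25%: 1.753 × 0.246 × 0.354 = 0.153, a factor of 1.165. A ratio of 1.00 gives an upper limit of 1.165 (passes); 1.10 gives 1.28 (fails).
- CV 15%: factor 1.097; 1.10 gives 1.21 (passes).

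Conversely, a true ratio of 0.90 inflated by 1.10 would show as 0.99.

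**The case against.** The case on the other side is substantial.

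- **Tmax in this trial is unknown.** The 0.5 h value comes without dose, food state or formulation. Here dispersible tablets follow a light meal (Protocol 7 and 8), whose effect on amodiaquine Tmax is not given. The source paragraph is also uneven. It calls the metabolite Cmax 19-fold the parent's, although 181/32 is 5.7. It also reports no amodiaquine in plasma at 8 h, where the fitted profile still has 10-18% of Cmax. This stands, and it is why the size must be a range. A reader might take 13-15% as established, but the documents support it only if the peak is at 0.5 h under trial conditions.
- **The decision is a within-subject ratio on one common schedule.** With equal absorption the error largely cancels. The 1.75 h figure is a value in malaria patients, not an effect of co-administration, and the Introduction discusses only hepatic enzymes. If the peak with amodiaquine alone is already at 1.0 h, a move to 1.75 h gives only 1.02-1.06. A reader might infer that the trial's ratio will be biased upwards, but nothing in the documents shows that artemether-lumefantrine slows amodiaquine absorption. Equally, nothing there establishes that it does not.
- **The plan may partly cover this.** A per-dose reading of SAP 3.5.2 would make doses 1 and 5 nearly unbiased, but doses 2 to 4 would each be about 18-26% low. Tmax is tabulated alone against combination, so a large shift should be visible. SAP 3.1.4 allows NONMEM. None of these is tied to the 80-125% test.

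**Conclusion.** The point holds in conditional form. Table 2 leaves four of six amodiaquine peaks unsampled if the peak is near 0.5 h, and no planned step corrects for it. Full-profile AUC is then about 13-15% low in the matched model. It is about 4-10% low with a peak at 1.0-1.75 h, 7% in a one-compartment model and 9-23% over the documented SDs. CL/F is overstated to match.

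The ratio is affected only if absorption differs between regimens. Slower absorption alone would then move it to about 1.06-1.11, enough to change the no-interaction conclusion at some plausible CVs and not at others. The point concerns amodiaquine AUC and, with less certainty, artemether AUC. It does not undermine Cmax, lumefantrine or desethylamodiaquine.

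**What to change.** **SAP (wording only).** In 3.5.2, state whether AUC is per dose or over the full profile. For amodiaquine and artemether, prespecify AUC0-8h and AUC48-60h, the two densely sampled intervals, as a sensitivity analysis of the 80-125% test. Show it beside the full-profile AUC and the Tmax comparison. It should not replace the full AUC: as absorption slows, this partial AUC itself falls by about 1-6% at Tmax 1.0-1.75 h and by up to about 13% with a 1 h lag. Describe full-profile CL/F and V/F of amodiaquine as approximate.

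**Sampling, if not yet started.** Put early post-dose samples after the 8, 24 and 36 h doses in all three regimens, for example by moving the 3, 51 and 56 h samples to 8.5, 24.5 and 36.5 h. The count stays at 35, no blood is added, and none of the three moved samples has a paired ECG. The AUC error falls to about −3%, and the ratio error to about 1% when only the absorption rate slows. This is not a complete cure: with a 0.5 h lag the moved samples precede any rise and the ratio is about 0.94. The cost is less detail near the desethylamodiaquine (3.4 h) and lumefantrine (6-8 h) peaks.

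A fuller option adds 0.25, 0.5 and 1 h samples after the 8, 24, 36 and 60 h doses. That is 11 extra (61 h already exists), or 11 mL in each single regimen and 22 mL in the combination. It brings the AUC error to about zero, but a 1 h lag would also call for a sample near 1.5 h.

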6.4.1. Pharmacokinetic Samples (Plasma Matrix)

Blood samples (1 mL for regimen 1, 2 and 2 mL for regimen 3) will be collected into properly labeled 2 mL sodium heparin blood collection tubes at the study times shown in Table 2.

Sample Handling

Upon collection, blood samples will be centrifuged for 7 minutes at 2000g at 4°C. After centrifugation, the plasma of each sample will be transferred via pipette to a pre-labeled sample storage tube and stored upright until analyzed.

Sample Storage

Samples will be immediately frozen in the storage tubes in the upright position in a non-self-defrosting freezer at -70°C or lower.

6.5. Storage of Genetic Samples

If the subject consents for genetic sample collection and testing, the genetic samples (10 mL) will be collected.

In case of any abnormal metabolisms in individuals, genotyping for the identification of polymorphisms of Cytochrome 450 (e.g. CYP2D6, CYP3A4) and other enzymes related to drug metabolism will be performed. DNA will be extracted from blood and PCR will be performed. SNP typing will be used to determine the gene mutation by comparing subject with normal metabolism activities to subject with abnormal metabolism activities. These tests will determine if there is any genetic abnormality. Such data may be useful in predicting those who may not obtain the full therapeutic or prophylactic benefit of study drugs.

Genetic samples will be stored (approximately 10 years) and tested at the Molecular Tropical Medicine Laboratory, Faculty of Tropical Medicine, Mahidol University. In case that particular genetic test is unable to be performed at Molecular Tropical Medicine Laboratory, Faculty of Tropical Medicine, Mahidol University, genetic sample may be transferred to another institute with subject consent.

A MTA (Material Transfer Agreement) will also be in place before any samples are sent to another institution for testing.

Any proposed plans to use this sample other than for the purposes of this study will be submitted to the IRB/EC prior to any genetic testing being performed.

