All study drugs are metabolized in the liver. Artemether and lumefantrine are primarily metabolized via CYP3A4 (19). Artemether metabolism through CYP3A4 produces an active metabolite, dihydroartemisinin (DHA) that contributes substantially to its antimalarial activity. Artemether is also a CYP3A4 inducer, while lumefantrine inhibits CYP2D6 (20). The clearance of amodiaquine and metabolism to its main metabolite, N-desethylamodiaquine, is catalyzed primarily by CYP2C8 (21). As some of these drugs share the same enzymes or have effects on the enzymes for other drug metabolism, the co-administration may result in clinically significant drug-drug interactions that can cause unanticipated adverse reactions or therapeutic failures. To evaluate whether such effects take place, we propose to co-administer these drugs in this healthy volunteer study.

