2.2. Secondary Objectives

- To characterize the pharmacokinetic properties of artemether-lumefantrine and amodiaquine when given alone and in combination.
- To evaluate the safety and tolerability of co-administered artemether-lumefantrine and amodiaquine.

• To investigate pharmacogenetic polymorphisms affecting drug levels of artemetherlumefantrine and amodiaquine and their metabolites.

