3.2. Secondary Endpoints

- Elimination clearance (CL/F), terminal elimination half-life (t1/2) and apparent volume of distribution (Vd) of artemether, lumefantrine and amodiaquine and their metabolites when given alone and in combination.
- Safety and tolerability parameters, including adverse events, electrocardiographic changes, vital signs and biochemical assessments.
- Pharmacogenetic polymorphisms in the case of unusual metabolizer.

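### Genotyping waits for an undefined abnormal metabolism, so the objective on polymorphisms affecting drug levels can be answered only weakly and selectively

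*Protocol*

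**What the plan says.** The objective in Protocol 2.2, repeated in SAP 2.3, carries no restriction to particular subjects: "To investigate pharmacogenetic polymorphisms affecting drug levels of artemetherlumefantrine and amodiaquine and their metabolites".

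The endpoint in Protocol 3.2 is narrower: "Pharmacogenetic polymorphisms in the case of unusual metabolizer". SAP 2.4 has the same restriction.

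Protocol 6.5 gives the procedure:
- Sampling depends on consent, not on drug levels: "If the subject consents for genetic sample collection and testing, the genetic samples (10 mL) will be collected".
- Typing is conditional: "In case of any abnormal metabolisms in individuals, genotyping for the identification of polymorphisms of Cytochrome 450 (e.g. CYP2D6, CYP3A4". The list of enzymes stays open: "and other enzymes related to drug metabolism will be performed".
- The comparison is made "by comparing subject with normal metabolism activities to subject with abnormal metabolism activities".

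On amodiaquine, Protocol section 1 (potential interactions through hepatic metabolism) states: "The clearance of amodiaquine and metabolism to its main metabolite, N-desethylamodiaquine, is catalyzed primarily by CYP2C8". The same paragraph gives CYP3A4 as the main enzyme for artemether and lumefantrine. It mentions CYP2D6 only as an enzyme that lumefantrine inhibits.

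SAP section 3 describes the pharmacokinetic and safety analyses. It contains no pharmacogenetic analysis.

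**The concern.** The objective asks whether genotype affects exposure. Under 6.5, what is seen of a subject's metabolism decides whether genotype is looked at. I take that to be judged from the concentration data, since the documents name no other basis. Carriers whose levels look ordinary do not start the process, and the groups to be compared are formed by the outcome.

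The trigger is also undefined. No analyte, parameter, period (alone or combination) or cut-off is given, so it can be settled after the concentrations are known, in an open-label study. The number and choice of normal comparators are equally open.

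A secondary objective is at stake: it may end as remarks on one or two outliers, or as nothing. The primary comparison of AUC and Cmax is not affected.

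**Working it through.** The documents give no figure for this objective, so there is none to reproduce. The sample-size paragraph (Protocol 12.4) concerns the bioequivalence test only.

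**1. Texts side by side**

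| Element | Protocol | SAP |
|---|---|---|
| Objective | 2.2: all polymorphisms affecting drug levels | 2.3: same |
| Endpoint | 3.2: unusual metabolizers only | 2.4: same |
| Trigger | 6.5: abnormal metabolism, undefined | none |
| Comparators | 6.5: normal subjects, number and choice unstated | none |
| Analysis | none beyond the comparison in 6.5 | none |

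**2. How often would a carrier start the genotyping?** (illustration)

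Assumptions, none from the documents: a subject is flagged if log AUC lies more than 2 SD from the non-carrier mean; one parameter of one analyte is used; between-subject CV is 40-60%; log AUC is normal.

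- SD of log AUC: σ = √ln(1+CV²), which is 0.385 at 40% and 0.555 at 60%.
- Shift in SD units for a carrier with fold-change f: δ = ln(f)/σ.
- P(flag) = Φ(δ−2) + Φ(−δ−2).

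| f | δ at CV 40% | P(flag) | δ at CV 60% | P(flag) |
|---|---|---|---|---|
| 1.3 | 0.681 | 9.7% | 0.473 | 7.0% |
| 1.5 | 1.052 | 17.3% | 0.731 | 10.5% |
| 2.0 | 1.799 | 42.0% | 1.250 | 22.7% |

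The background rate with no genotype effect is 2Φ(−2) = 4.55%, so part of each figure is chance.

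**3. How often would nobody be flagged?**

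Under the same rule, with no genotype effect and independent subjects, P(none of 16) = 0.9545^16 ≈ 47%. The chance of at least one flag is 53%. With three carriers at 1.5-fold (a further assumption) it is 1 − 0.9545^13 × (1−P(flag))³, or 61% at CV 60% and 69% at CV 40%.

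**4. What can the outcome-formed comparison show at best?**

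Suppose all 16 are typed, every abnormal subject is a carrier and no normal subject is. The two-sided Fisher p is then 1/C(16,k) for k abnormal subjects:
- k = 1: 1/16 = 0.0625
- k = 2: 1/120 = 0.0083
- k = 3: 1/560 = 0.0018

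With one abnormal subject, even perfect separation misses 5%. That is the level SAP 3.1 sets for comparing proportions, although the SAP does not say it applies here.

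**5. What would typing everyone give?**

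The carrier share is c = 1−(1−q)² for an assumed variant allele frequency q, with n = 16 and full consent.

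| q | Expected carriers (16c) | P(at least 1) | P(at least 2) |
|---|---|---|---|
| 1% | 0.32 | 27.5% | 4% |
| 5% | 1.56 | 80.6% | 47.1% |
| 10% | 3.04 | 96.6% | 83.7% |
| 20% | 5.76 | 99.9% | 99.2% |

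A comparison of exposure by genotype becomes possible for common variants. For rare ones there may be no carrier.

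**The case against.** The strongest defence is that endpoint and procedure agree with each other. Both concern the unusual metabolizer, and whether such subjects carry variants that normal subjects lack can be examined descriptively. Samples are kept for about 10 years, so wider typing stays possible. That much stands. The wider objective is still listed in both documents, and neither document commits to the wider typing.

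Several stronger readings are tempting but not supported:

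- **Only abnormal subjects are typed.** Section 6.5 describes a comparison with normal subjects, so some of them must be typed. What is missing is how many and which.
- **CYP2C8 is left out.** The enzymes are given as examples, the list is open-ended, and it names CYP3A4, the main enzyme for artemether and lumefantrine. CYP2C8 is unnamed, not excluded.
- **The objective cannot be answered at all.** That follows only if nobody is judged abnormal.
- **Some 83-93% of carriers would go untyped.** This is the complement of the flagging probabilities at 1.3- and 1.5-fold. It is the share who would not themselves trigger typing. An unflagged carrier may still be typed as a comparator once somebody else is flagged. Also, six analytes are measured, alone and in combination, so each subject may have several chances to be flagged.
- **Any association found must be exaggerated.** Selecting extremes inflates fold-effect estimates, but a comparison of genotype frequencies between abnormal and normal subjects is not necessarily biased.
- **A genotype effect that differs between the alone and combination periods would go unrecognised.** Nothing in 6.5 confines abnormal metabolism to one period.

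**Conclusion.** The concern holds in this form. The objective is broader than its endpoint, the trigger and the comparators are undefined, and no analysis is planned. The question as worded would therefore be answered only weakly and selectively, and not at all if no subject is judged abnormal. These points rest on the text alone.

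The gene list is a lesser point. CYP2C8 deserves to be named, since the protocol makes it the primary amodiaquine enzyme. CYP2D6 is named although the protocol does not describe it as clearing any study drug.

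The sizes are illustrative: a 7-10% chance at 1.3-fold and 11-17% at 1.5-fold that a carrier triggers genotyping, and about 47% that nobody does so when genotype has no effect. They depend on the assumed 2 SD rule and a single parameter; the carrier figures also depend on the assumed CV of 40-60%. The matter is worth correcting because the remedy is cheap. It does not bear on the primary result.

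**What to change.** - **Protocol 3.2 and 6.5, SAP 2.4:** genotype every consenting subject from the sample already collected, whatever the drug levels, so that the endpoint matches the objective. Name CYP2C8 (amodiaquine) and CYP3A4/5 (artemether, lumefantrine); the clause on other enzymes can stay.
- **SAP section 3:** add a descriptive table by genotype, with confidence intervals, of log AUC in the alone period and of the combination/alone ratio.
- **If the outlier approach is kept instead:** define abnormal or unusual metabolism (analyte, parameter, period, cut-off) and the choice of comparators before concentrations are seen, and narrow the objective in Protocol 2.2 and SAP 2.3 to match.

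The cost is assays on at most 16 samples, with no new blood draw or visit. The consent wording, which is not in the public documents, must be checked to see that it covers typing of all subjects. At n = 16 the result stays descriptive, and rare variants may have no carriers.
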